7. RESEARCH DESIGN & METHODS

This is a single center, investigator initiated, nonrandomized, open-label, proof of concept study of PDT with blue light and topical Levulan® in the treatment of actinic cheilitis.

7.1 SUBJECT RECRUITMENT

Patients with a diagnosis of actinic cheilitis who have been seen at the outpatient dermatology clinic at Dartmouth Hitchcock Medical Center will be contacted by telephone by study coordinator(s), investigator(s), or designee in order to recruit study participants after discussing the study in detail.

7.2 SCREENING & ELIGIBILITY

Male and female subjects \geq 18 years of age with a diagnosis of actinic cheilitis will be asked to participate in this study after the objectives, methods, and potential hazards of the study have been fully explained, and they have signed the informed consent form. The Principle Investigator will be responsible for keeping a record of all subjects who sign an informed consent form for entry into this study. A total of 20 subjects will be enrolled in this study.

7.2.1 INCLUSION CRITERIA

- Must be able to understand and voluntarily sign an informed consent form
- Must be male or female ≥ 18 years of age at the time of consent
- Must be able to adhere to the study visit schedule and other protocol requirements
- Must have a diagnosis of actinic cheilitis by histopathological evaluation of biopsy specimen or clinical presentation

7.2.2 EXCLUSION CRITERIA

- Inability to provide voluntarily consent or mentally incompetent
- No active herpes labialis lesions
- Subjects with any condition which places the subject at unacceptable risk if he/she were to participate in the study, or confounds the ability to interpret data from the study
- Subjects with any other skin condition that might affect the evaluation of the study disease
- Pregnant or breastfeeding female subjects

- Subjects who have used any investigational medication within one month prior to study entry
- Subjects who have been previously exposed to PDT and/or topical Levulan® therapy
- Subjects who have used local therapy (e.g. cryotherapy) or topical treatment (e.g.
 5% fluorouracil) within three months of study entry
- Subjects who have used an oral photosensitizing drug (e.g. Declomycin®) within six months of study entry
- Subjects who are currently using photosensitizing agents (e.g. thiazides, tetracyclines, fluoroquinolones, phenothiazines, and sulfonamides) because of the risk of augmented photosensitivity
- Subjects who are frequently exposed to ultraviolet radiation (e.g. lifeguards, construction workers, frequent sunbed users, etc.)
- Subjects with a history of cutaneous photosensitization, porphyria, hypersensitivity to porphyrins, or photodermatosis
- Subjects with a known hypersensitivity to δ -aminolevulinic acid
- Subjects who are immunocompromised

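### The herpes labialis item in the exclusion list is worded as an entry requirement, so its direction is reversed as written (section 7.2.2 and Synopsis)

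*Combined protocol and SAP*

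**What the plan says.** Under the heading "7.2.2 EXCLUSION CRITERIA" the second item is "No active herpes labialis lesions". The Synopsis (section 3) gives the same item, in the same words and the same position, under Exclusion Criteria.

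The neighbouring items are built differently. One, for example, is "Subjects with a known hypersensitivity to δ -aminolevulinic acid", which names the feature that keeps a subject out. Two general items in the same list rest on the investigator's judgement. One covers any condition that creates unacceptable risk or confounds interpretation of the data. The other is "Subjects with any other skin condition that might affect the evaluation of the study disease".

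The inclusion list (section 7.2.1) has four items: consent, age, ability to follow the schedule, and diagnosis. The last is "Must have a diagnosis of actinic cheilitis by histopathological evaluation of biopsy specimen or clinical presentation". None concerns herpes.

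The Schedule of Assessments (section 4) has the criteria checked at screening and again at baseline. Section 7.3 requires eligibility to be confirmed before baseline procedures.

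**The concern.** An exclusion criterion removes a subject when the statement is true of that subject. Here the statement is true of someone who has no active lesions, so the written rule points the opposite way from the rest of the list.

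This is an operative rule, not background text. It is applied at two visits and decides who may be treated. Section 7.6 counts a protocol violation among the reasons to consider discontinuing a subject, and section 11.2 sets out how deviations are handled. A criterion that says the reverse of what is presumably meant leaves the record of who was eligible open to argument.

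The treated and assessed site is the lip, and section 9.2.2 grades swelling, vesiculation, erosion and crusting there. Whether lesions present at entry are excluded therefore bears on how those grades are read, particularly in an open-label study with no control group.

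**Working it through.** No arithmetic applies; the check is a comparison of texts.

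1. **Count the items.** Section 7.2.2 has 14 bullets. Thirteen name an excluding state, for example pregnancy, earlier PDT, current photosensitizing agents or immunocompromise. The first, on inability to consent, contains a negative idea but still names the state that excludes. The herpes item is the only one of the 14 whose truth describes a subject fit to enter.

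2. **Apply it literally.**
   - Active lesions absent: the statement is true, so the exclusion is met and the subject is out.
   - Active lesions present: the statement is false, so this exclusion is not met. The subject is neither admitted nor removed by this item; the other 13 still apply.

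3. **Look for a correcting text.** The Synopsis copy is identical, so neither place corrects the other. The inclusion list has no herpes item, and herpes appears nowhere else in the protocol text available for review.

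4. **Rule out a reading error.** The sentence is complete and identical in two separate places, with no redaction or broken table at either.

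5. **See what else would catch a subject with active lesions.** The two general items could exclude such a subject. They depend on the investigator's judgement, whereas the herpes item is explicit. They limit the consequence but leave the item itself uncorrected.

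**The case against.** The best defence is that nobody would apply the words literally. The study has one center and recruits from its own dermatology clinic, baseline includes a dermatologic exam, and the intent can be guessed at once from the rest of the list. That largely stands as an argument about consequence, but it does not make the written rule correct.

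Four stronger readings are tempting, and the documents do not support them.

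- *The protocol admits subjects with active herpes labialis.* Failing to meet one exclusion admits nobody, and the two general items could still remove such a subject.
- *The item contradicts the exclusion of other skin conditions.* Two exclusions can both apply without contradiction. Read literally together they would leave very few people eligible, which is a further sign that the literal reading is not meant.
- *All 20 planned subjects would be ineligible.* This follows only if the item is applied literally to 20 subjects without active lesions, which is not a credible way for the study to run. One wrongly enrolled subject would be 1/20 = 5% of the sample, but nothing in the documents gives a probability that this happens.
- *Audits would flag every correctly enrolled subject.* Section 12.3 requires access for audits and inspections; it describes no check of eligibility criterion by criterion.

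**Conclusion.** The point holds as a drafting and consistency error of low severity: the polarity of one eligibility item is reversed in section 7.2.2 and in the Synopsis. It is not a debatable design choice, and it alters no endpoint, sample size or analysis.

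The reversal follows from the text alone. That the practical effect is small rests on two assumptions: that the investigators will read the intent rather than the words, and that the judgement-based exclusions will be used where needed. Both are plausible at a single center, but the protocol does not guarantee either. The frequency of misclassification cannot be estimated from the documents, so no figure is offered.

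**What to change.** The sponsor should confirm what was intended and then make the item agree with the list in which it stands, in both section 7.2.2 and the Synopsis. Two equivalent edits would do this:

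- remove the negation, so that the item names the excluding state as the other 13 do; or
- move the sentence unchanged to the inclusion list, in section 7.2.1 and in the Synopsis.

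The documents describe no eligibility checklist; if a screening or case report form repeats the item, it should be changed to match.

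The edit is a few words in two places. Under section 11.1 an amendment needs the agreement of the Principal Investigator, review by the drug supplier and, unless it is treated as administrative, IRB/IEC approval before it is implemented. An administrative change is still submitted to the IRB/IEC for information. Schedule, sample size and analysis are unaffected.

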7.3 VISIT SCHEDULE & ASSESSMENTS

The study will consist of a screening visit, up to three scheduled treatments, and two scheduled office visits. There can be a three-day window period for each scheduled visit in order to accommodate the subject's schedule and unforeseen scheduling conflicts.

- Visit 1 (Screening): Subjects can be screened for the study up to two weeks before Visit 2 (Baseline). During screening, the study will be reviewed, written informed consent obtained, and eligibility confirmed. If applicable, the washout from prohibited medications or treatments will be determined at this visit.
- 2. Visit 2 (Baseline): Following signed, written informed consent and confirmation of eligibility, all subjects will have their lips photographed. Medical history, dermatologic exam, urine pregnancy test (if applicable), review of concomitant medications, clinical evaluations, and tolerability assessments will be performed at this visit. Study medication application to clean skin will be followed by a ninety minute incubation period under occlusion. Subsequently, patients will be exposed to blue light therapy for 16 minutes and 40 seconds. Post-therapy

- assessments will be performed afterwards, as well as education on appropriate sun protection methods.
- 3. Visits 3-4: Subjects will return every six weeks for up to two additional treatments. Treatment will be discontinued once the patient has achieved clinical clearance. Tolerability assessments, study medication application, blue light therapy, post-therapy assessments, and photographs will be performed.
- 4. Visit 5-6 (End of Study): Subjects will return 12 and 24 weeks after the last treatment for clinical evaluations, tolerability assessments, and photographs.

7.4 DURATION OF TREATMENT

After the screening visit, subjects will receive in-office treatments every six weeks for 12 weeks for up to a total of 3 treatments. Treatment will be discontinued once the patient has achieved clinical clearance. Each subject will then be followed for 24 weeks after the last treatment visit. In total, each subject will be part of the study for approximately 36 weeks.

7.5 RISK TO SUBJECTS

PDT often invokes a transient local skin reaction, including increased erythema, edema, and/or scaling. These symptoms typically dissapate after one to two weeks, and are usually well tolerated if strict sun protection and avoidance are heeded; however, certain patients may have a more significant adverse response to PDT, especially if they are taking concomitant photosensitizing drugs (i.e. doxycycline, topical/oral retinoids, etc.). It is therefore of uptmost importance that patients who are currently using photosensitizing agents or frequently exposed to ultraviolet radiiation are exclused from study participation in order to minimize the risk of adverse events.

No patient identifying information will be documented on any of the research materials, except for the informed consent paperwork and the Subject ID Key (see Section 9.1). Only the study investigators and assigned research personel will know the identity of each study subject, but they will not disclose this information unless necessitated by the law. The informed consent paperwork and all of the study research materials (i.e. demographic questionnaires, data collection sheets, etc.) will be held in a secure and

confidential file for at least three years after the conclusion of this study, in accordance with the rules put in place by the IRB.

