8.4 POST-EXPOSURE SKIN CARE

Subjects will be given verbal and written post-treatment instructions to clean treatment sites with warm water and CeraVe® Facial Cleanser®, and to apply topical petrolatum ointment until any weeping or crusting has subsided. Subjects will also apply chapstick with sun protection. All subjects will be instructed to avoid direct sun exposure and to apply a sun block with at least a sun protection factor (SPF) of 30 (Neutrogena® SPF 100) for at least 48 hours after each treatment.

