9. CLINICAL ASSESSMENTS

Efficacy and safety assessments during the treatment phase of the study will be done at the intervals specified in Section 4. The same investigator should complete the evaluations for a given subject throughout the study; however, if the assigned investigator is not available, another investigator with overlapping experience with the subject can complete the evaluation.

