9.2.2 PRE & POST-TREATMENT SAFETY ASSESSMENTS

A study physician will complete post-treatment assessments based upon visual observation of *swelling, vesiculation/pustulation, erosion/ulceration, erythema, flaking/scaling,* and *crusting.* The assessment will be based upon the scaling system below:

Swelling	Grade 0: not present
	Grade 1: slight, lesion specific edema
	Grade 2: palpable edema extending beyond individual lesions

	Grade 3: confluent or visible edema
	Grade 4: marked swelling, very easily noticeable from a
	distance
Vesiculation/Pustulation	Grade 0: not present
	Grade 1: only vesicles
	Grade 2: <50% pustules with or without vesicles
	Grade 3: > 50%, but <75% pustules with or without vesicles
	Grade 4: >75% pustules with or without vesicles
Erosion/Ulceration	Grade 0: not present
	Grade 1: lesion specific erosion
	Grade 2: erosion extending beyond individual lesions
	Grade 3: erosion >50%
	Grade 4: black eschar or ulceration
Erythema	Grade 0: not present
	Grade 1: slightly pink <50%
	Grade 2: pink or light red >50%
	Grade 3: red 50-75%
	Grade 4: severe redness, >75%, very easily noticeable from a
	distance
Flaking/Scaling	Grade 0: not present
	Grade 1: isolated scale, specific to lesions
	Grade 2: scale <50%
	Grade 3: scale >50%, but <75%
	Grade 4: scale >75%, very easily noticeable from a distance
Crusting	Grade 0: not present
	Grade 1: isolated crusting
	Grade 2: crusting <50%
	Grade 3: crusting >50%
	Grade 4: crusting >75%, very easily noticeable from a distance

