9.3.3 DERMATOLOGY LIFE QUALITY INDEX

Subjects will be asked to complete the Dermatological Life Quality Index (DLQI) at every scheduled visit except for screening. These questionnaires should be completed by the subject before any other procedures or assessments are performed. If the subject is physically unable to complete the questionnaires, study personnel/staff may assist

him/her. Relatives and friends of the subject may not under any circumstances assist the subject with the questionnaire. The subject will initial and date his/her entries in the designated area of the Case Report Form (CRF) for each questionnaire. The CRF will serve as the source documentation for this study. The DLQI questionnaire is as follows:

Dermatological Life Quality Index

The aim of this questionnaire is to measure how much your skin problem has affected your life OVER THE LAST WEEK. Please check one response for each question.

Question	Response
1. Over the last week, how itchy, sore, painful, or stinging has	□ 1. Very much
your skin been?	
	□ 2. A lot
	2 A Pul
	□ 3. A little
	□ 4. Not at all
2. Over the last week, how embarrassed or self-conscious have	
	□ 1. Very much
you been because of your skin?	□ 2. A lot
	2.71.00
	□ 3. A little
	□ 4. Not at all
3. Over the last week, how much has your skin interfered with	□ 1. Very much
you going shopping or looking after your home or garden ?	
	□ 2. A lot
	□ 3. A little
	□ 4. Not at all
	⊔ 4. NOt at all
	□ 5. Not relevant
4. Over the last week, how much has your skin influenced the	□ 1. Very much
clothes you wear?	

	□ 2. A lot
	□ 3. A little
	□ 4. Not at all
	□ 5. Not relevant
5. Over the last week, how much has your skin affected any	□ 1. Very much
social or leisure activities?	□ 2. A lot
	□ 3. A little
	□ 4. Not at all
	□ 5. Not relevant
6. Over the last week, how much has your skin made it difficult	□ 1. Very much
for you to do any sport ?	
	□ 2. A lot
	□ 3. A little
	□ 4. Not at all
	□ 5. Not relevant
7. Over the last week, has your skin prevented you from	□ 1. Yes
working or studying?	
	□ 2. No
	□ 3. Not relevant
	□ 1. A lot
If "No", over the last week how much has your skin been a	

problem at work or studying?	□ 2.A little
	□ 3. Not at all
8. Over the last week, how much has your skin created problems	□ 1. Very much
with your partner or any of your close friends or relatives ?	
	□ 2. A lot
	2.4.15.1
	□ 3. A little
	□ 4. Not at all
	1 4. NOT at all
	□ 5. Not relevant

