9.3.4 TWO-DAY POST-TREATMENT TELEPHONE FOLLOW-UP VISIT

Patients will be asked to rate *redness, swelling,* and *dryness* on the scale below. The scales will be read to the patient over the phone.

Redness	Grade 0: None
	Grade 1: Minimal redness, only a little noticeable

	Grade 2: Mild redness, easily noticeable and involving less than 1/3 of the face
	Grade 3: Moderate redness, easily noticeable and involving between 1/3 and 2/3 of the face
	Grade 4: Severe redness, very easily noticeable from a distance, and involving over 2/3 of the face
Swelling	Grade 0: None
_	Grade 1: Minimal swelling, only a little noticeable
	Grade 2: Mild swelling, easily noticeable and involving less than 1/3
	of the face
	Grade 3: Moderate swelling, easily noticeable and involving
	between 1/3 and 2/3 of the face
	Grade 4: Severe swelling, very easily noticeable from a distance,
	and involving over 2/3 of the face
Dryness of Skin	Grade 0: None
	Grade 1: Minimal dry skin, only a little noticeable
	Grade 2: Mild dry skin, easily noticeable and involving less than
	1/3 of the face
	Grade 3: Moderate dry skin, easily noticeable and involving
	between 1/3 and 2/3 of the face
	Grade 4: Severe dry skin, very easily noticeable from a distance,
	and involving over 2/3 of the face

Additionally the subject will be asked the open-ended question, "Have you had any problems since leaving our office after your last appointment?" The study coordinator will then record each subject's response in the appropriate source document.

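### Between the treatment day and the next clinic visit, one subject-reported call on day 2 is the only rating of local reactions; three of the six physician-graded signs have no graded item on it, so reactions may be understated

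*Combined protocol and SAP*

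**What the plan says.** Safety is part of the single objective (Section 6), and the synopsis makes tolerability a secondary endpoint. Section 7.5 names erythema, edema and scaling as the transient local reaction and adds: "These symptoms typically dissapate after one to two weeks". Section 8.4 has subjects "apply topical petrolatum ointment until any weeping or crusting has subsided", so weeping and crusting are foreseen at home.

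Section 9.2.2 sets the physician rating: "A study physician will complete post-treatment assessments based upon visual observation of" swelling, vesiculation/pustulation, erosion/ulceration, erythema, flaking/scaling and crusting, each graded 0 to 4. The Section 4 schedule marks these signs at Visits 2 to 6 only. On visit timing, Section 7.3 says "Subjects will return every six weeks for up to two additional treatments" and then "Subjects will return 12 and 24 weeks after the last treatment for clinical evaluations, tolerability assessments, and photographs".

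Section 9.3.4 adds a telephone contact two days after treatment. The subject grades redness, swelling and dryness from 0 to 4 ("The scales will be read to the patient over the phone") and answers one open question about problems since the appointment. Section 4 has no column for this call; it places the redness, swelling and dryness items at Visits 2 to 6. Section 9 states: "Efficacy and safety assessments during the treatment phase of the study will be done at the intervals specified in Section 4".

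The synopsis excludes the listed local skin reactions from its definition of adverse events. Section 10 records as adverse events only new signs outside the expected effects of PDT, and it names crusting and blistering among the events associated with PDT.

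**The concern.** The physician's grades come from shortly after illumination and then from weeks later. Vesicles, erosions or crusts that develop at home in between have no graded item anywhere. Because the adverse event rules set expected reactions aside, the tabulation of adverse events would not reliably recover them. The study has one arm, so no control group measured on the same schedule could put the grades in context. A report of mostly low grades could then reflect when the ratings were made as much as how the treatment was tolerated.

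**Working it through.** **Inputs.** Treatment visits 6 weeks apart, follow-up visits 12 and 24 weeks after the last treatment, and a three-day visit window (Section 7.3). The window's direction is not stated; I take it as plus or minus 3 days. Reaction period of one to two weeks, so up to day 14 (Section 7.5). Call on day 2 (Section 9.3.4). 20 subjects (Section 7.2), at most 3 treatments each (Section 7.4).

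**The plan's own figure.** With three treatments the last is at week 12. Then 12 + 12 = week 24 and 12 + 24 = week 36, which match Visits 5 and 6 in Section 4.

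**Treatment to next physician rating.**

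| Interval | Nominal | Window at one end | Window at both ends | Shortest gap after day 14 |
|---|---|---|---|---|
| Visit 2 to 3, Visit 3 to 4 | 6 × 7 = 42 days | 39 to 45 | 36 to 48 | 36 − 14 = 22 days |
| Visit 4 to 5 | 12 × 7 = 84 days | 81 to 87 | 78 to 90 | 78 − 14 = 64 days |

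**Ratings inside the period, per treatment.** Physician ratings on days 1 to 14: 0. Subject ratings on days 1 to 14: 1, on day 2. Ratings of any kind on days 3 to 14: 0.

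**Signs covered by the call.** Redness matches erythema, swelling matches swelling, and dryness is a loose match for flaking/scaling. Vesiculation/pustulation, erosion/ulceration and crusting have no item: 6 − 3 = 3 signs ungraded between the treatment day and the next visit.

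**Anchors.** In Section 9.3.4, grade 2 means less than one third of the face, grade 3 one to two thirds, and grade 4 more than two thirds. A reaction confined to the lip covers less than a third of the face, so on extent it could hardly be graded above 2, however severe. The physician scales in Section 9.2.2 are anchored differently, to lesions and percentages among other things, so equal numbers on the two scales do not mean the same thing.

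**Exposure.** 20 × 3 = 60 treatments at most. This is a ceiling, because treatment stops once a subject has cleared.

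**The case against.** The strongest reply is that the plan does rate the reaction it describes. A reader might infer that the one-to-two-week reaction falls wholly between ratings. It does not: Section 7.5 ties that period to erythema, edema and scaling, and the day-2 call rates the first two directly and the third loosely. A reader might also infer that, by the protocol's own account, vesicles, erosions and crusts have gone by the next visit. Section 10 calls crusting and blistering transient but gives no duration, and its list of PDT events does not mention erosion. Both corrections stand.

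Other routes exist. The answer to the open question goes into the source documents whether or not it becomes an adverse event, subjects are questioned openly at each visit, and a reaction beyond the expected profile could still be recorded as an adverse event. These routes reduce the loss of information. They do not yield grades for the three missing signs.

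It is tempting to add pain and the DLQI to the gap. The pain endpoint concerns illumination itself and is measured around it (synopsis, Section 9.3.2). For the DLQI, "Subjects will be asked to complete the Dermatological Life Quality Index (DLQI) at every scheduled visit except for screening"; its one-week recall would miss the reaction period, but Section 4 lists it as an efficacy measure. Neither fails in its stated role.

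Finally, this is a small proof-of-concept study, and the heading of Section 9.3.4 fixes the call's timing even though the schedule omits it. That limits the weight of the point. It does not supply the missing ratings.

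**Conclusion.** The point holds in a limited form and is worth fixing. After each treatment, the only rating before the next clinic visit is one subject-reported call on day 2, covering three signs on scales built for the face. Three of the six physician-graded signs have no grade from the treatment day until day 36 at the earliest (nominally day 42, or day 84 after a Visit 4 treatment). Nothing is rated on days 3 to 14, so duration and any later peak are unmeasured.

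The tolerability endpoint may therefore understate local reactions. The documents do not support saying that it will: they do not state when reactions peak, and the day-2 call captures part of the picture. The day counts rest on reading the visit window as plus or minus 3 days at both ends; the conclusion is the same with the window at one end or none.

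**What to change.** - Add the two-day call to Section 4 after each treatment, and reconcile this with the row that now places redness, swelling and dryness at the clinic visits.
- Add graded items to the call for crusting or weeping, blistering and open sores.
- Re-anchor all the call's scales to the lip or treated area.
- Report the worst call grade per treatment beside the physician's treatment-day grade, as two separate sources. Do not pool them, because the raters and the anchors differ.
- If the next visit also asks for the worst reaction since the last treatment, label the answer as supportive recall data. Recall over 6 to 12 weeks is too weak to carry the endpoint or to date resolution.

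The cost is a few more questions at a call already planned and a CRF change, with no new visit or staff. The added grades would be the subject's rather than a physician's. Days 3 to 14 would still have no rating made at the time, and the report should say so.
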